8.1. Primary Efficacy Endpoint

As defined in Section 3.2.1, the primary efficacy endpoint is percent change from baseline in PVR immediately before PEA at Visit 2. The PVR assessment from Visit 2 needs to be within 7 days prior to PEA. Assessments out of the time frame will be considered invalid and be treated as missing. In the case of patients who do not undergo PEA, the PVR at Visit 2 will be treated as missing.

The null hypothesis is that there is no difference between the treatment groups in percent change from baseline in PVR immediately before PEA at Visit 2, and the alternative is that the difference is not zero. The primary efficacy analyses will be conducted using the ITT set. Similar analysis will be repeated for the PPS as the supportive analysis.

The difference in the percent change from baseline in PVR immediately before PEA at Visit 2 between riociguat and placebo will be tested using the 2-sample Wilcoxon rank-sum test.

Analysis of covariance (ANCOVA) with baseline value as the covariate will be employed to test the null hypothesis as a supportive analysis. Residuals for percent change from baseline in PVR will be generated by using PROC GLM procedure with baseline value as the covariate. A quantile-quantile (Q-Q) plot of residuals with p-value from Shapiro-Wilk test will be presented to test the normality of the residuals.

To check the effect of missing values on the robustness of the primary analysis, the primary analysis will be repeated using the baseline observation carried forward approach for missing PVR values immediately before PEA at Visit 2.

The PVR will be measured at pre-PEA visit (Visit 2) and at the 6-month follow-up visit (Visit 4). Observed values, changes from baseline and percent change from baseline will be provided for PVR using descriptive statistics by treatment group and scheduled visit.

Boxplot will be used to present the percent change from baseline in PVR by treatment group and scheduled visit. The upper (lower) edge of the box represents the 75th (25th) percentile. A horizontal line in the box interior represents the median. Above the box a vertical line indicates the region from the 3rd quartile to the 95% percentile; below the box a vertical line indicates the region from the 1st quartile to the 5% percentile. Values outside the whiskers are displayed by a distinct marker.

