8.2.1. Pulmonary Vascular Resistance (PVR)

The difference in the percent change from baseline in PVR at Visit 4 between riociguat and placebo will be tested using the 2-sample Wilcoxon rank-sum test for the PEA set and the PPS.

PVR assessment at Visit 4 will use the nominal visit information collected in eCRF without considering the time window because PVR status is expected to be stable after PEA.

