8.2.2. Composite Clinical Endpoints

Composite clinical endpoints from randomisation to Visit 4 will be tabulated by treatment group containing the number and percentage of patients with an event as well as the number of event for the PEA set and the PPS. The Fisher exact test will be utilised to test the proportion difference along with the Clopper-Pearson exact CI when applicable. For analysis based on the ordinal response of functional class, the row mean score from the Cochran Mantel-Haenszel test will be used to test the response difference between groups.

Composite clinical endpoints include following clinical endpoints:

- All-cause death

All deaths that happen after randomisation until the date of Visit 4, 6 months after the PEA, will be included.

- PH-related hospitalisation

All PH-related hospitalisation except the in-hospital care after PEA from randomisation until 6 months after PEA will be included.

- Need for PAH-targeted therapy

All PAH-targeted therapy from randomisation until 6 months after PEA will be included.

- Functional class unchanged or worse

When comparing the functional class assessment at Visit 1 with the functional class assessment at other visits, the same class will be defined as unchanged, and a higher class will be defined as worse. The worst case after treatment will be used.

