8.2.3.2. Surgery-related Complications

Surgery-related complications at Visit 2 from the perioperative findings will be tabulated by treatment group in a descriptive way for the PEA set, presenting the number and percentage of patients for each symptom. The Fisher exact test will be utilised to test the proportion difference along with the Clopper-Pearson exact CI.

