8.3. Exploratory Efficacy Endpoints

Exploratory efficacy endpoints are defined in Section 3.2.3. No formal assessment of difference between treatment groups will be performed for any of the exploratory efficacy endpoints. The difference between treatment groups in exploratory efficacy endpoints will be estimated with 95% CIs to quantify the treatment effect.

Summary tables presenting observed values and changes from baseline for NT-proBNP measurement concentration (pg/mL), cardiac output (L/min), cardiac index (L/min/m²), mRAP (mmHg), mPAP (mmHg), and PAWP (mmHg) will be provided for each treatment group by scheduled visits using descriptive statistics. The difference in the change from baseline between treatment groups with 95% CIs will be estimated non-parametrically using Hodges-Lehmann estimation of location shift in the tables. The analyses will be based on the PEA set and the PPS.

Hospital length of stay in days and ICU length of stay in days will be summarised using descriptive statistics. The difference between treatment groups with 95% CI will be estimated non-parametrically using Hodges-Lehmann estimation of location shift in the table. The analyses will be based on the PEA set.

Time from start of ICU stay to end of mechanical ventilation (in hours) will be analysed using the Kaplan Meier method. Median and quartiles in days and associated 95% CI will be calculated using the LOGLOG transformation. All patients stayed in ICU who do not have end date of mechanical ventilation will be censored at the time of discharged from the ICU. The analyses will be based on the PEA set.

Proportion of in-hospital mortality will be summarised using the frequency counts and percentages for the PEA set. Proportion difference between treatment groups along with the Clopper-Pearson exact CI will be provided

The proportion of patients who need PAH-targeted therapy immediately after PEA to Visit 4 will be summarised using the frequency counts and percentages for the PEA set and the PPS. Proportion difference between treatment groups along with the Clopper-Pearson exact CI will be provided.

WHO functional class will be summarised by scheduled visit for each treatment group. Shift table of baseline functional class versus functional class at each postbaseline scheduled visit will be provided. The analyses will be based on the PEA set and the PPS.

9. Safety Analysis

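### SAP 8.3 attaches Clopper-Pearson, a one-proportion interval, to two between-arm differences, and SAP 8.1 and 8.2.1 name no between-arm estimate with CI for percent change in PVR

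*SAP*

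**What the plan says.** **Proportions.** SAP 8.3 opens with a commitment: "The difference between treatment groups in exploratory efficacy endpoints will be estimated with 95% CIs to quantify the treatment effect". For in-hospital mortality, and again for PAH-targeted therapy between PEA and Visit 4, it specifies: "Proportion difference between treatment groups along with the Clopper-Pearson exact CI will be provided".

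Two secondary analyses use related wording. SAP 8.2.2 (composite) has "The Fisher exact test will be utilised to test the proportion difference along with the Clopper-Pearson exact CI when applicable", and SAP 8.2.3.2 (surgery-related complications) has "The Fisher exact test will be utilised to test the proportion difference along with the Clopper-Pearson exact CI".

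**PVR at Visit 2 (primary).** SAP 8.1 states that the difference in percent change "between riociguat and placebo will be tested using the 2-sample Wilcoxon rank-sum test". An ANCOVA "with baseline value as the covariate will be employed to test the null hypothesis as a supportive analysis" is added. There is also a repeat with baseline carried forward, descriptive statistics by arm and visit, and a boxplot.

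**PVR at Visit 4 (secondary).** SAP 8.2.1 says only that the difference "will be tested using the 2-sample Wilcoxon rank-sum test for the PEA set and the PPS". Protocol 7.8.2 says Visit 4 follows the primary approach, which would include the ANCOVA. SAP section 11, the list of changes, does not withdraw that.

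**Other haemodynamic variables.** For NT-proBNP, cardiac output, cardiac index, mRAP, mPAP and PAWP, SAP 8.3 says the between-arm difference in change from baseline "will be estimated non-parametrically using Hodges-Lehmann estimation of location shift", with 95% CIs. PVR is not on that list.

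**The concern.** Clopper-Pearson inverts the exact binomial test for a single proportion. Its limits lie between 0 and 1, so it cannot describe a difference, which may be negative. A programmer following SAP 8.3 must either substitute a method that the SAP does not name or print per-arm limits beside a bare difference. The second course leaves out the interval that the same section promises.

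For PVR the matter is one of omission. Protocol section 7 calls all analyses exploratory, and SAP 4.1 says the sample size is not based on power. In such a trial the size of the effect and its uncertainty are the most useful result. As written, mPAP, cardiac index and NT-proBNP receive a between-arm estimate with CI, while the primary endpoint receives p-values and by-arm summaries. If the estimator is chosen only after unblinding, the main published effect size is not pre-specified.

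**Working it through.** **Inputs from the documents.** 88 randomised 1:1 with a target of 80 completers (Protocol 4.3.3; SAP 4.1); two-sided 5% and 95% CIs (SAP 4); perioperative mortality of 4.7% (Protocol 1.1). The figure of 88 reproduces as 80 × 1.10 = 88; dividing instead, 80/0.90 gives 89. I use 80/2 = 40 per arm. The plan states no precision, SD or event rate of its own, so **all counts and SDs below are assumed**.

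**Step 1. What each interval gives for proportions.** The Clopper-Pearson limits for x/n are the 2.5% quantile of Beta(x, n−x+1) and the 97.5% quantile of Beta(x+1, n−x). For a difference d = p1 − p2, Newcombe combines the Wilson limits (l, u) of the two arms:

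- lower = d − √[(p1 − l1)² + (u2 − p2)²]
- upper = d + √[(u1 − p1)² + (p2 − l2)²]

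Worked case, 4/40 vs 12/40, in percent: the Wilson limits are 3.96–23.05 and 18.07–45.43.

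- lower = −20 − √[(10 − 3.96)² + (45.43 − 30)²] = −20 − 16.6 = −36.6
- upper = −20 + √[(23.05 − 10)² + (30 − 18.07)²] = −20 + 17.7 = −2.3

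At 4.7% mortality, 0.047 × 40 = 1.88 deaths per arm would be expected, so the two mortality cases use small counts around that figure.

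| Assumed counts | Clopper-Pearson, arm 1 | Clopper-Pearson, arm 2 | Difference, points | Newcombe 95% CI | Miettinen-Nurminen 95% CI |
|---|---|---|---|---|---|
| Death 1/40 vs 3/40 | 0.1–13.2% | 1.6–20.4% | −5.0 | −17.5 to +6.5 | −17.8 to +6.4 |
| Death 1/40 vs 4/40 | 0.1–13.2% | 2.8–23.7% | −7.5 | −20.7 to +4.5 | −21.1 to +4.2 |
| PAH therapy 4/40 vs 12/40 | 2.8–23.7% | 16.6–46.5% | −20.0 | −36.6 to −2.3 | −37.3 to −2.5 |

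In the last row the per-arm intervals overlap from 16.6% to 23.7%, yet both difference intervals exclude zero (Fisher p = 0.048). Per-arm limits therefore do not stand in for an interval on the difference.

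**Step 2. What is missing for PVR.** With n per arm and normal percent changes, the half-width for a difference in means is 1.96 × SD × √(2/n). Dividing by √(3/π) = 0.977 approximates the Hodges-Lehmann half-width. With n = 40, √(2/40) = 0.2236. The simulation used 1,500 trials per setting, with coverage of 94–95%.

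| Assumed SD of percent change | Mean difference | Hodges-Lehmann, formula | Hodges-Lehmann, simulation |
|---|---|---|---|
| 15 | 6.6 | 6.7 | 6.8 |
| 20 | 8.8 | 9.0 | 9.1 |
| 25 | 11.0 | 11.2 | 11.4 |
| 30 | 13.1 | 13.5 | 13.7 |

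In simulated trials with a Wilcoxon p between 0.025 and 0.035, the average shift was −7.7 points (−14.6 to −0.8) at SD 15 and −15.4 points (−29.2 to −1.6) at SD 30. The same p-value goes with effects that differ twofold.

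**Step 3. Whether another section fills the gap.** SAP section 4 says that tests lead to 95% CIs. That fixes the confidence level but names no estimator. A rank-sum p-value has no interval until a location parameter is chosen, and the Hodges-Lehmann shift and the ANCOVA-adjusted mean difference are different parameters.

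**The case against.** The best case for the plan runs as follows.

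- **The sentence in 8.3 can be read as per-arm limits beside the difference, as in 8.2.2 and 8.2.3.2.** That reading is possible, and it is correct use of Clopper-Pearson. It can be programmed, but it leaves the difference without the CI promised at the start of 8.3. Sections 8.2.2 and 8.2.3.2 carry no such promise, so the wording there is milder.
- **Nothing is lost for binary endpoints.** Counts and denominators are tabulated, so a reader can compute any two-sample interval, and Newcombe and Miettinen-Nurminen differ little. This is true and limits the harm. It does not make the stated method the right one.
- **The PVR estimates follow from the planned tests.** Both intervals are natural by-products. From n, mean and SD by arm, which SAP 8.1 provides at Visit 4 as well, a reader can rebuild an approximate mean-difference CI that is almost as narrow as the Hodges-Lehmann interval under normality. That stands. The Hodges-Lehmann shift that matches the Wilcoxon test and the baseline-adjusted difference cannot be rebuilt from those summaries.
- **The examples are chosen.** The 4 vs 12 case lies near the significance boundary; with 4/40 vs 10/40 the Newcombe CI is −31.4 to +1.9 and the overlapping per-arm limits would not mislead. Also, 40 per arm comes from the completer target, whereas in-hospital deaths are counted in the PEA set. Both remarks are fair. The figures illustrate the problem and do not predict results.

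**Conclusion.** The point holds. In SAP 8.3 the named interval is wrong for a difference, or, on the charitable reading, the promised interval is absent. For percent change in PVR, no between-arm estimate with CI is specified at either visit, although SAP 8.3 specifies one for the exploratory haemodynamic variables.

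The consequence is confined to estimation and reporting. The Wilcoxon test, alpha, sample size and data collection are untouched. The 8.3 wording needs correction; the PVR addition is a nearly free gain for the primary question. That Clopper-Pearson does not apply to a difference, and that no PVR estimator is named, depends on none of the assumed counts or SDs. Only the sizes shown do.

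**What to change.** 1. In SAP 8.3, and for consistency in 8.2.2 and 8.2.3.2, report the difference in proportions with one named two-sample 95% CI (Newcombe, Miettinen-Nurminen or exact unconditional), chosen before unblinding. Keep Clopper-Pearson for single-arm rates and say so.
2. In 8.2.2 and 8.2.3.2, state that the p-value comes from Fisher and the interval is for estimation, because the two can disagree. At an assumed 4/40 vs 11/40, for example, Newcombe gives −34.0 to −0.2 while Fisher p = 0.083.
3. In SAP 8.1 and 8.2.1, add the Hodges-Lehmann shift with 95% CI for percent change in PVR beside the Wilcoxon p-value.
4. In SAP 8.1, report the baseline-adjusted mean difference with 95% CI from the planned ANCOVA. In 8.2.1, state whether that ANCOVA also applies at Visit 4, as Protocol 7.8.2 implies; if it does not, list the change in SAP section 11.

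The cost is a few sentences and standard SAS options. Hodges-Lehmann estimation and the ANCOVA are already in the plan, and no new data are needed.

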7.8.3 Analyses of Exploratory Efficacy Endpoint

No formal assessment of difference between treatment groups will be performed for any of the exploratory efficacy endpoints. All exploratory efficacy endpoints will be presented mainly in a descriptive way. If deemed necessary, the difference between both treatment groups in exploratory efficacy endpoints will be estimated with 95% CIs to quantify the treatment effect.

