- When frequency counts are presented, the percentage will be suppressed when the count is zero in order to draw attention to the non-zero counts. A row denoted “Missing” will be included in count tabulations where specified on the shells to account for dropouts and missing values. Percentages will be based on the total number of patients in the respective analysis set unless otherwise specified.
- Unless otherwise specified, statistical tests will be 2-sided and performed using a 5% significance level, leading to 95% (2 sided) confidence intervals (CIs). Modelling techniques will be used in an exploratory sense. No adjustments for multiplicity are made.
- Partial dates will be imputed based on the rules specified in Appendix 13.4.
- All laboratory data will be reported by using the International System of Units.
- Unless otherwise specified, the baseline will be defined as the last valid assessment, including assessments from the unscheduled visit, prior to the study drug administration.
- A Visit 2 assessment is considered as valid only when the assessment is completed within 7 days prior to PEA. For assessments at Visit 4, the nominal visit collected in electronic case report form (eCRF) will be used in the analysis. This rule is applicable to all endpoints derived by the visit.
- By-patient listings will be created for each eCRF module for all screened patients. Patients will be identified in the listings by patient number. If data are to be summarised by visit, the visit name collected on the eCRF page will be used.
- All analyses will be conducted using SAS® software Version 9.3 or later (SAS Institute Inc, Cary, North Carolina).

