4.1. Sample Size

A total of 88 patients, accounting for a 10% dropout rate, will be randomly assigned into riociguat or placebo groups at a ratio of 1:1 in the study. The sample size for this study is not based on the required statistical power to test any specific hypothesis but feasibility to initially assess the safety and efficacy of riociguat on preoperative pulmonary haemodynamics in patients with operable CTEPH.

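### SAP 8.3 promises a 95% interval for the between-arm difference, but for its two binary exploratory endpoints it names only Clopper-Pearson, which covers a single proportion

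*SAP*

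**What the plan says.** SAP 8.3 rules out formal comparison of the arms on exploratory endpoints and then commits to estimation: "The difference between treatment groups in exploratory efficacy endpoints will be estimated with 95% CIs to quantify the treatment effect". Protocol 7.8.3 has the same aim, but only if deemed necessary; the SAP drops that condition.

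For the continuous exploratory endpoints and the lengths of stay, SAP 8.3 names a suitable two-sample method, the Hodges-Lehmann estimate of location shift. It then turns to two binary endpoints. The first is in-hospital mortality. The second is introduced so: "The proportion of patients who need PAH-targeted therapy immediately after PEA to Visit 4 will be summarised using the frequency counts and percentages". Each is followed by the same sentence: "Proportion difference between treatment groups along with the Clopper-Pearson exact CI will be provided".

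Clopper-Pearson also appears with two secondary endpoints. For the composite, SAP 8.2.2 has "The Fisher exact test will be utilised to test the proportion difference along with the Clopper-Pearson exact CI when applicable", which repeats protocol 7.8.2. For surgery-related complications, SAP 8.2.3.2 has "The Fisher exact test will be utilised to test the proportion difference along with the Clopper-Pearson exact CI".

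No interval for a difference between two proportions is named anywhere in the protocol or SAP.

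**The concern.** Clopper-Pearson inverts a one-sample binomial test. It takes one count out of one denominator and returns limits for that one proportion; it has no two-sample form. A programmer who follows SAP 8.3 literally can print one interval per arm, which leaves the difference without the interval promised, or can improvise something from the two sets of limits.

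This matters more here than in a trial built around a powered test. The sample size is set by feasibility, the methods are mainly descriptive, and no formal test is planned for these two endpoints. The interval for the difference is therefore the only planned statement of how much the data can rule out. If the method is left open, it will be chosen at programming or after unblinding, which works against the SAP's stated purpose of fixing the methods beforehand.

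**Working it through.** The documents give no numerical interval to reproduce and no expected counts by arm. The check is therefore a reading of the text, followed by an illustration on assumed counts.

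**Text, side by side**

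- SAP 8.3, opening: a 95% interval for the difference, for exploratory endpoints.
- SAP 8.3, in-hospital mortality and PAH-targeted therapy: the difference, with Clopper-Pearson as the only interval named. The method cannot deliver what the opening requires.
- SAP 8.2.2 and 8.2.3.2: a Fisher test of the difference, accompanied by Clopper-Pearson. These are secondary endpoints, so the 8.3 commitment does not govern them, and neither section says what the interval is for.

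**Inputs**

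- Randomised: 88 at 1:1, so 88/2 = 44 per arm (SAP 4.1).
- Target completers: 80, so 80/2 = 40 per arm (protocol 4.3.3).
- Assumed operated patients: 42 per arm, between those two figures.
- Assumed events: 4 v 2 for in-hospital death and 16 v 10 for PAH-targeted therapy.
- Confidence level: two-sided 95% (SAP Section 4).

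**Formulas**

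- Clopper-Pearson, one arm: lower limit = Beta quantile (0.025; x, n−x+1); upper limit = Beta quantile (0.975; x+1, n−x).
- Improvised subtraction: (L1 − U2) to (U1 − L2), using the Clopper-Pearson limits.
- Newcombe: with Wilson limits l and u per arm and d = p1 − p2, lower = d − √[(p1−l1)² + (u2−p2)²]; upper = d + √[(u1−p1)² + (p2−l2)²].
- Miettinen-Nurminen: the values of d at which the score statistic, with restricted maximum-likelihood variance and the factor N/(N−1), equals ±1.96.

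**Worked case, 4/42 v 2/42**

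- Difference: 9.52% − 4.76% = 4.76 points.
- Clopper-Pearson: 4/42 gives 2.66% to 22.62%; 2/42 gives 0.58% to 16.16%. These are two intervals, and neither is for the difference.
- Subtraction: 2.66 − 16.16 = −13.5; 22.62 − 0.58 = 22.0.
- Newcombe: Wilson limits are 3.77% to 22.07% and 1.32% to 15.79%. Lower = 4.76 − √(5.75² + 11.03²) = −7.7; upper = 4.76 + √(12.55² + 3.44²) = 17.8.

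**Both cases, in percentage points (widths from unrounded limits)**

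| Counts | Difference | Subtracted limits (width) | Miettinen-Nurminen (width) | Newcombe (width) |
|---|---|---|---|---|
| 4/42 v 2/42 | 4.8 | −13.5 to 22.0 (35.5) | −7.7 to 18.1 (25.9) | −7.7 to 17.8 (25.4) |
| 16/42 v 10/42 | 14.3 | −15.9 to 42.3 (58.2) | −5.7 to 33.3 (39.0) | −5.4 to 32.6 (38.0) |

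Width ratios against Miettinen-Nurminen: 35.5/25.9 = 1.4 and 58.2/39.0 = 1.5. Against Newcombe: 35.5/25.4 = 1.4 and 58.2/38.0 = 1.5.

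**Coverage at 40 per arm, by exact binomial enumeration**

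| Assumed true rates | Subtracted limits | Newcombe |
|---|---|---|
| 4.7% / 4.7% | 99.99% | 98.7% |
| 5% / 10% | 99.9% | 96.2% |
| 15% / 30% | 99.7% | 95.2% |
| 30% / 30% | 99.7% | 95.2% |

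The subtraction is thus not a 95% interval.

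**What a valid interval would show.** At the perioperative mortality of 4.7% cited in protocol 1.1, 40 patients give 0.047 × 40 = 1.9, or about 2 deaths per arm. For 2/40 v 2/40, Miettinen-Nurminen gives −12.3 to +12.3 points.

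**The case against.** The strongest reply is that the sentence in SAP 8.3 can mean a point estimate of the difference printed beside exact limits for each arm. Per-arm Clopper-Pearson limits are valid, so on this reading nothing is computed wrongly. That is fair, but it does not rescue 8.3: the section's opening still requires an interval for the difference, and no method for one would then be named.

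The same reply succeeds for the composite and the complications. Both are tabulated as number and percentage by arm, the 8.3 commitment is limited to exploratory endpoints, and the Fisher test supplies the comparison. A reader might infer that these two endpoints also have an invalid interval. The documents do not support that; they leave the interval's target unstated.

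Two other stronger readings are tempting:

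- That every binary endpoint is affected. It is not: all-cause death (SAP 8.2.5) and withdrawal (SAP 8.2.6) carry no Clopper-Pearson wording.
- That the planned interval is 1.4 to 1.5 times too wide. No section tells anyone to subtract opposite limits, and the counts are assumed. Had it been done, the interval would overstate uncertainty, so it would not create a false signal.

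It is also true that all analyses are exploratory, and that a valid interval could be calculated later from the reported counts. This limits the harm but does not supply the pre-specified method.

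**Conclusion.** The concern holds for two endpoints, in-hospital mortality and PAH-targeted therapy after PEA. SAP 8.3 promises an interval for the difference and names a method that cannot give one. This rests on the text alone and needs no assumed figures. For the composite and surgery-related complications the wording is ambiguous: valid per arm, but then without an interval for the effect.

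The ratio of 1.4 to 1.5 describes one possible improvisation, on assumed counts with 42 patients per arm. The certain consequence is narrower: the interval method is unspecified.

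The primary PVR analysis, the Fisher p-values, the Hodges-Lehmann intervals and the sample size do not change. The point is modest in consequence but worth correcting, because the correction is nearly free.

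**What to change.** - SAP 8.3: for in-hospital mortality and PAH-targeted therapy, report the risk difference with one named two-sample 95% interval. Miettinen-Nurminen, Newcombe or an exact unconditional interval would each serve; choose one and state it. Keep Clopper-Pearson for the per-arm proportions only, and say so.
- SAP 8.2.2 and 8.2.3.2: use the same wording, so that the composite and the complications have a per-arm interval and an effect interval, each clearly labelled.
- SAP Section 11: record the change from protocol 7.8.2, which has the Clopper-Pearson wording for the composite. For complications, protocol 7.8.2 plans only a descriptive table, and Section 11 does not list the Fisher test and interval that SAP 8.2.3.2 adds; the same entry can cover this.

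The cost is four edited sentences, one Section 11 entry and a programming option. No new data are needed. The change should be made before database lock and unblinding.
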